12.6.1.1 Sensitivity Analyses

Missing data sensitivity analyses to Exploratory Efficacy Endpoints 3.1, 3.3, 3.4 and 3.8 to 3.15 may be performed as per imputation strategies (a) and (b) as described [Section 12.3.3.1](#).

12.6.1.2 Subgroup Analyses

Subgroup analyses to Exploratory Efficacy Endpoints 3.1, 3.3, 3.4 and 3.8 to 3.15 will be performed as per [Section 12.5.2](#).

12.6.2 Analysis for Change and Percent Change from Baseline at Week 52 Exploratory Efficacy Endpoints 3.9, 3.11, 3.13, 3.15 and 3.16

An ANCOVA model will be used to analyses Exploratory Endpoints 3.9, 3.11, 3.13, 3.15 and 3.16. The absolute or change or percent change from baseline (placebo-controlled baseline; see section 8.3.9) to 52 weeks will be the dependent variable. The ANCOVA model will include terms for treatment group (0: placebo, 1: tildacerfont); the randomization strata: sex (0: male, 1: female) and baseline GC dose (in HCe, 0: < 40 mg/day, 1: \geq 40 mg/day); and baseline GC type (0: short-acting, 1: intermediate-acting or combination) as categorical explanatory variables. The difference in LSmeans between randomised treatment groups at Week 52 along with the associated CI and 2 sided p-value will be extracted.

Further, a paired t-test will be used to compare the change from tildacerfont-baseline to 52 weeks on treatment with tildacerfont.

In terms of descriptive statistics, for each type of analysis, the change from baseline will be reported by treatment group for the reported value and change from baseline value, and percent change from baseline value (if applicable) will also be presented.

12.6.2.1 Sensitivity Analyses

Missing data imputation strategies (a) and (b) may be applied to Exploratory Efficacy Endpoints 3.9, 3.11, 3.13, 3.15 and 3.16 as described [Section 12.3.3.1](#).

12.6.2.2 Subgroup Analyses

Subgroup analyses may be performed for Exploratory Efficacy Endpoints 3.9, 3.11, 3.13, 3.15 and 3.16 as per [Section 12.5.2](#).

12.6.3 Exploratory Efficacy Endpoints 3.5 to 3.7 and 3.17 to 3.20, Responder Analyses

Exploratory Efficacy Endpoints 3.5 to 3.7 and 3.17 to 3.20 are responder endpoints and will be analyzed in the same manner as Secondary Efficacy Endpoint 2.1.

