To evaluate the safety of tildacerfont in subjects with CAH	Adverse events (AEs), serious adverse events (SAEs)
Study Design	
This is a study with a 2-part treatment period that will evaluate the potential of tildacerfont to reduce GC burden in adult subjects with classic CAH who have LLD \leq A4 \leq 2.5x ULN and are on supraphysiologic doses of GC therapy (\geq 30 mg/day and \leq 60 mg/day in HCe). The first 24 weeks of the treatment period will be a randomized, double-blind, placebo-controlled study in which subjects are randomized in a 1:1 ratio to receive either placebo or tildacerfont at 200 mg once daily (QD). All subjects will receive open-label tildacerfont at 200 mg QD during the remaining 52 weeks of the treatment period. An optional Open-Label Extension Period will provide an open-label treatment with tildacerfont at 200 mg QD for up to 240 weeks.	
Refer to the study schematic provided in Section 1.2 .	
Study Periods	
This study will consist of the following periods:	

• A \leq45-day Screening Period for confirmation of eligibility
○ Optional A4 Screening Visit○ Screening information captured within 45 days of the start of Day 1 in this study (particularly screening information transferred from Spruce Biosciences Study SPR001-203 to this study) will be used to determine eligibility and fulfill screening requirements for this study.	
In Germany, screening information from Spruce Biosciences Study SPR001-203 is not permitted to be transferred to determine study eligibility.	

- A 6 or 12-week *Glucocorticoid Conversion Period* (Week -12 to either Week -6 or Week -2 [± 3 days]) for subjects on dexamethasone at the initial Screening Visit who agree to convert to a non-dexamethasone regimen as determined by their physician.
- A 76-week, 2-part *Treatment Period*
 - The 24-week *Placebo-Controlled Treatment Period* (Day 1 to Week 24) will be randomized, double-blind, and placebo-controlled. Subjects will be randomized in a 1:1 ratio to receive either placebo or tildacerfont at 200 mg QD.
 - The 52-week *Open-Label Period* (day after Week 24 to Week 76) will provide subjects who complete the Placebo-Controlled Treatment Period with 52 weeks of open-label treatment with tildacerfont 200 mg QD.

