9.1 Statistical Hypotheses

Efficacy endpoints at Week 24 will be evaluated using the following hypothesis-testing schema: The tildacerfont treatment group will be compared with the placebo treatment group. The null hypothesis is that there is no difference in the mean change from baseline to Week 24 in GC dose in HCe. The alternative hypothesis will be that there is a difference between the treatment groups.

Efficacy endpoints after 52 weeks of tildacerfont treatment will be evaluated using the following hypothesis-testing schema: The Week 52 value will be compared with the baseline value. The null hypothesis will be that there is no difference between the Week 52 and baseline values. The alternative hypothesis will be that there is a difference.

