9.4 Statistical Analyses

9.4.1 General Considerations

All individual data will be listed as measured. All statistical summaries and analyses will be performed using SAS software (SAS Institute Inc, Cary, North Carolina, USA).

Unless otherwise specified, continuous adrenal biomarkers (A4, 17-OHP, ACTH) will be summarized using a 11-point descriptive statistics (i.e., n, mean, standard deviation [SD], median, 25% quartile [Q1], 75% quartile [Q3], minimum, maximum, geometric mean, geometric coefficient of variance [CV%], 95% confidence interval [CI] for geometric mean [including geometric mean ratio and its 95% CI]). Continuous data aside from (A4, 17-OHP and ACTH) will

be summarized using an 8-point descriptive summary (n, mean, SD, median, Q1, Q3, minimum, and maximum).

Categorical data will be summarized using the frequency of events and percentage of total events.

Data will be presented by treatment group. Changes in primary, secondary, and exploratory endpoints will be analyzed over time, with change from baseline summarized for each post-baseline time point measured.

All efficacy analyses will be conducted using the ITT Population as the primary analysis set and using a 2-sided alpha of 0.05.

For missing data, a retrieved dropout approach will be used in which missing endpoint data for subjects who discontinued early will be imputed using data collected from subjects after discontinuation of study drug.

Secondary and exploratory analyses that evaluate the change from baseline in all subjects after 52 weeks of tildacerfont treatment will combine the subjects randomized to tildacerfont Day 1 to Week 52 data with subjects randomized to placebo tildacerfont treatment data from Week 24 to Week 76.

Any changes to the protocol-specified analyses will be pre-specified in the SAP prior to database lock.

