8.3.17 Testicular Adrenal Rest Tumor Volume

For each TART assessment, the total number of TARTs will be captured as well as the size (lesion volume) of each TART individually. The lesion volume for each detectable TART will be calculated as follows using the formula for an ellipsoid (length \times width \times thickness \times 0.52). The total lesion volume for all detectable TARTs will be the endpoint for analysis.

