12.5.1.1 Statistical Modeling and Testing

The Secondary Efficacy Endpoints are all binary ‘response’ endpoints will be analyzed using logistic regression modelling.

The model for each endpoint will include the responder indicator as the dependent variable; treatment group (0: placebo, 1: tildacerfont); the randomization strata: sex (0: male, 1: female) and baseline GC dose (in HCe, 0: < 40 mg/day, 1: ≥ 40 mg/day); and baseline GC type (0: short-acting, 1: intermediate-acting or combination) as categorical explanatory variables; and, for

Secondary Efficacy Endpoint 2.3, the baseline number of CV risk factors will also be included as a categorical covariate.

An exact score test derived from the logistic regression model, equivalent to an exact CMH test on small sample sizes, will be used to provide the 2-sided p-value to determine whether proportion of responders is different between the tildacerfont treatment group and the placebo treatment group at Week 24. If the logistic model does not converge, a Fisher's exact tests corresponding to the tildacerfont treatment group compared to placebo will be utilized.

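### SAP 12.6.3 tests the Week 52 responder endpoints as tildacerfont against placebo, but the contrast is 52 against 28 weeks on tildacerfont

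*SAP*

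**What the plan says.** **The model.** SAP 12.6.3 states that endpoints 3.5 to 3.7 and 3.17 to 3.20 "are responder endpoints and will be analyzed in the same manner as Secondary Efficacy Endpoint 2.1". For endpoint 2.1, SAP 12.5.1.1 specifies a logistic regression: "The model for each endpoint will include the responder indicator as the dependent variable; treatment group (0: placebo, 1: tildacerfont"). Its exact score test is to "determine whether proportion of responders is different between the tildacerfont treatment group and the placebo treatment group at Week 24".

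**Treatment after Week 24.** Protocol 1.1: "All subjects will receive open-label tildacerfont at 200 mg QD during the remaining 52 weeks of the treatment period".

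**The protocol on 52 weeks.** For efficacy after 52 weeks of tildacerfont, Protocol 9.1 says: "The Week 52 value will be compared with the baseline value". Protocol 9.4.1 says that such analyses "will combine the subjects randomized to tildacerfont Day 1 to Week 52 data with subjects randomized to placebo", the latter contributing their on-drug data from Week 24 to Week 76. Protocol 9.4.6 reads the tildacerfont arm at Week 52 and the placebo arm at Week 76. SAP 8.3.9.2 defines a matching baseline, the last value before the first tildacerfont dose.

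**The continuous Week 52 endpoints.** SAP 12.6.2 extracts "The difference in LSmeans between randomised treatment groups at Week 52" and adds a paired t-test from the tildacerfont baseline to 52 weeks on tildacerfont.

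**TART.** SAP 5.1.3.11 defines 3.17 and 3.18 as change in total volume, and SAP 8.3.17 says: "The total lesion volume for all detectable TARTs will be the endpoint for analysis". SAP 12.6.3 lists both as responder endpoints. Protocol Section 3 defines both as the proportion of men with a reduction in volume.

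**The concern.** Endpoints 3.5, 3.6, 3.7 and 3.20 are Week 52 endpoints, and at Week 52 nobody is on placebo. The treatment term in the model can vary only if it means randomised arm, so what it estimates is the effect of starting tildacerfont 24 weeks earlier. If the output carries the label placebo, a small or null difference can be mistaken for absence of effect when it may mean that the switched arm has caught up.

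The question the protocol raises for 52 weeks, how subjects fare after that time on drug, has a paired analysis for the continuous endpoints in SAP 12.6.2. The responder endpoints in SAP 12.6.3 have no counterpart.

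The same sentence also takes in the two TART endpoints, which the SAP defines elsewhere as continuous and for which its responder table (Table 9) gives no rule. A programmer could not implement 3.17 or 3.18 from the SAP alone.

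**Working it through.** **1. Time on drug.** By the schedule of activities, Week 24 is Day 169 and Week 52 is Day 365. The placebo-randomised arm has had 365 − 169 = 196 days = 28 weeks of tildacerfont at Week 52, against 52 weeks in the other arm. It reaches 52 weeks at Week 76 (76 − 24 = 52).

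**2. The plan's own power figure.** Protocol 9.2 gives 45 per arm, 30% on placebo, a difference of 33 points (so 63% on tildacerfont), two-sided 0.05, and at least 90% power. With p̄ the mean of the two rates:

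power = Φ{ [d − 1.96·√(2p̄(1−p̄)/n)] / √[(p₁(1−p₁) + p₂(1−p₂))/n] }

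For 0.30 against 0.63, p̄ = 0.465 and the two standard errors are 0.1052 and 0.0992. Then (0.33 − 1.96 × 0.1052)/0.0992 = 1.249 and power is 0.894, which reproduces the stated figure to within a point.

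**3. What happens if the switched arm catches up.** This is an illustration only. The rates are planning values for a different, Week 24 endpoint (a reduction of at least 5 mg/day with A4 ≤ ULN), and 63% at Week 52 is assumed. Let the switched arm close a share f of the gap, so that its rate is 0.30 + 0.33f.

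| f | Switched-arm rate | Difference | z-test power | Fisher exact power |
|---|---|---|---|---|
| 0 | 0.300 | 0.330 | 0.894 | 0.839 |
| 0.25 | 0.3825 | 0.2475 | 0.656 | 0.561 |
| 0.50 | 0.465 | 0.165 | 0.347 | 0.264 |
| 0.75 | 0.5475 | 0.0825 | 0.121 | 0.084 |

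At f = 1 the true difference is zero and any rejection is a type I error. The Fisher column sums the probability of all outcome pairs with p ≤ 0.05. SAP 12.5.1.1 names an exact score test with Fisher as fallback, so the exact column is nearer to what would be run, though without covariates.

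**4. What a pooled on-drug estimate would give.** At 63%, the approximate 95% half-width is 1.96·√(0.63 × 0.37/n): 0.100 for n = 90 and 0.141 for n = 45. The larger n is a ceiling. Endpoint 3.5 needs a baseline cardiovascular risk factor, 3.7 needs a baseline dose ≤ 35 mg, and dropout reduces all four.

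**5. TART, place by place.** Protocol Section 3 gives a proportion; SAP 5.1.3.11 and 8.3.17 give a continuous volume; SAP 12.6.3 gives a responder analysis; SAP Table 9 has no TART rule. The endpoint 2.1 model includes sex, which is constant in a male-only endpoint. SAP 4.3.1.5 schedules follow-up ultrasound at Weeks 24 and 76 in the Treatment Period. In SAP Table 12 the Week 76 window opens on Day 493 and the Week 52 window closes on Day 408, so the Week 76 scan cannot serve as a Week 52 value for 3.18.

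**The case against.** **The endpoints are worded for Week 52.** Endpoints 3.5, 3.6, 3.7 and 3.20 are defined at Week 52, whereas HOMA-IR, BMI, waist, body composition and BMD are defined after 52 weeks of tildacerfont. Protocol 9.4.6 applies its evaluation periods to select endpoints, and SAP 5.1.3.4 describes 3.5 as an effect of randomised treatment at Week 52. This stands: early against delayed start is a valid randomised contrast, and a reader should not infer that the protocol plainly requires pooling for these four endpoints. But neither Protocol 9.1 nor 9.4.6 contains a Week 52 comparison with placebo, and the SAP does not name the contrast for what it is.

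**Full catch-up is not assured.** A reader might infer that an effective drug must show no arm difference at Week 52. The documents do not support that. Adjustments are at most 5 mg/day HCe each, and before Week 52 the switched arm has only two on-drug A4 visits that can prompt one (Weeks 32 and 40). Nor do the documents say that a null result would be reported as no effect against placebo; SAP Table 10 assigns open-label records to tildacerfont.

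**TART as a responder endpoint is the protocol's definition.** A reader might infer that SAP 12.6.3 wrongly dichotomises 3.17. It matches the protocol. The defect is that the SAP contradicts itself and lacks the rule. The constant sex term is minor, since it drops out of the model.

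**The endpoints are exploratory.** They lie outside the Hochberg family in SAP 9.6. This limits the consequence but does not make the specification right.

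**Conclusion.** The point holds, limited to exploratory endpoints. Followed as written, SAP 12.6.3 tests 52 against 28 weeks on tildacerfont under a placebo coding and omits the analysis after 52 weeks on drug that SAP 12.6.2 gives to continuous endpoints. SAP Section 3 makes the SAP governing where it differs from the protocol, and SAP Section 14, which should list changes, is still to be completed, so nothing explains the difference.

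The 28 weeks follow directly from the schedule. The loss of power does not: it depends on borrowed Week 24 rates, 45 evaluable subjects per arm and an assumed degree of catch-up. It shows only that a non-significant Week 52 contrast would say little about efficacy. Primary and secondary conclusions are unaffected.

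For TART, the conflict over 3.17 and 3.18 is internal to the SAP, and 3.18 has no scheduled measurement at its stated time.

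**What to change.** 1. For 3.5, 3.6, 3.7 and 3.20, add the pooled proportion with an exact 95% CI after 52 weeks of tildacerfont: Week 52 for subjects randomised to tildacerfont, Week 76 for those randomised to placebo. Take the GC, A4, cardiovascular-risk and ≤ 35 mg subset baselines all from SAP 8.3.9.2. With Day 1 as baseline, GC reductions made on placebo would count as response to tildacerfont. State the denominators after the 3.5 and 3.7 restrictions and dropout.
2. Label the Week 52 between-arm contrasts in SAP 12.6.2 and 12.6.3 as early against delayed start (52 against 28 weeks on tildacerfont), and treat them as descriptive.
3. Choose one form for 3.17 and 3.18. Either analyse change in total volume, adjusted for baseline volume, by ANCOVA or rank ANCOVA that admits zero volumes (a log scale would lose men whose lesions resolve), or keep the protocol's proportion and add its rule to Table 9. Drop the sex term in either case.
4. Align 3.18 with the scheduled Week 76 scan and state the time on drug in each arm at that point (76 and 52 weeks).
5. Record these choices in SAP Section 14.

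The cost is SAP wording and programming. The responder data are already collected at Day 1 and Weeks 24, 52 and 76. The drawback is that the pooled estimate has no concurrent control, which the protocol already accepts for its 52-week analyses.

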12.6.3.1 Multiple Imputation for Missing Data

Subjects with missing response data Efficacy Endpoints 3.5 to 3.7 and 3.17 to 3.20 may have missing data imputed as per [Section 12.5.1.2](#).

12.6.3.2 Subgroup Analyses

Subgroup analyses may be performed for Exploratory Efficacy Endpoints 3.5 to 3.7 and 3.17 to 3.20 as per [Section 12.5.2](#).

12.6.4 Exploratory Efficacy Endpoint 3.2, Cumulative GC Dose

Cumulative GC dose in HCe over the period baseline to 24 weeks from randomization will be analysed via ANCOVA on the log scale. The model will include log cumulative GC dose in HCe over baseline to 24 weeks as the dependent variable; treatment group (0: placebo, 1: tildacerfont); the randomization strata: sex (0: male, 1: female) and baseline GC dose (in HCe, 0: < 40 mg/day, 1: ≥ 40 mg/day); and baseline GC type (0: short-acting, 1: intermediate-acting or combination) as categorical explanatory variables. The difference in LSmeans between

randomised treatment groups along with the associated CI and p-value will be extracted. The LSmeans and CI will be back transformed for the purposes of presentation.

The descriptive statistics in terms of the cumulative GC dose will be reported by treatment group and will include the geometric mean, log scale SE, Q1, Q3, min and max.

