All efficacy analyses will be conducted using the ITT Population as the primary analysis set. The primary analysis and secondary analyses conducted at Week 24 will compare the tildacerfont treated group to the placebo group. Additional secondary and exploratory analyses that evaluate the change from baseline in all subjects after 52 weeks of tildacerfont treatment will combine the subjects randomized to tildacerfont Day 1 to Week 52 data with subjects randomized to placebo tildacerfont treatment data from Week 24 to Week 76.

The primary efficacy endpoint is the absolute change from baseline in GC dose in HCe at Week 24. The analysis of the primary endpoint will be summarized using an exact score test for binomial proportions, as appropriate, or a chi-square-based test. Subjects with missing data will be assumed to be failure for the primary endpoint.

GC dose endpoints will be summarized using an analysis of covariance (ANCOVA) model with fixed covariates for baseline GC dose and treatment group. Sensitivity analyses that use multiple imputation will be conducted for missing GC dose data. The factors impacting the multiple imputation will include, but not be limited to, sex and baseline HCe group (<40 mg/day and \geq 40 mg/day).

The proportion of subjects meeting various responder definitions will be summarized in a similar manner as the primary endpoint.

Metabolic endpoints (HOMA-IR, body weight, and wc), QoL endpoint (SF-36), and BMD will be analyzed using a repeated measure mixed effects model with treatment and visit as fixed effects, subject as a random effect, and baseline score as a covariate if >2 timepoints are

[figure not shown]
assessed. If only the baseline timepoint and a single post-baseline timepoint are assessed for the endpoint, an ANCOVA model with baseline as a covariate will be used. There will be no imputation of missing data.

Endpoints during the optional Open-Label Extension Period will be summarized descriptively.

[figure not shown]
Safety Analyses

Safety analyses will be conducted on the Safety Population. All safety data will be presented in listings. Summary tables will be provided for concomitant medications, AEs, hematology and chemistry laboratory results, vital signs, and ECG findings. Safety data will be summarized by treatment group using frequency of event or descriptive statistics, as appropriate.

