4 STUDY DESIGN

This is a multi-center, randomized, double-blind, placebo-controlled, clinical study to evaluate the efficacy and safety of tildacerfont in reducing supraphysiologic glucocorticoid (GC) use in

adult subjects with classic CAH who have androstenedione (A4) ≤ 2.5 x upper limit of normal (ULN) and are on supraphysiologic doses of GC therapy (≥ 30 mg/day and ≤ 60 mg/day in hydrocortisone equivalents [HCe]) at baseline. This study consists of the following periods:

- ≤ 45 -day Screening Period will confirm subject eligibility
- Week -12 to either Week -6 or Week -2 Day -1 [± 3 days] GC Conversion Period, if applicable
- 76-week, 2-part Treatment Period
 - 24-week Placebo-Controlled Treatment Period
 - 52-week Open-Label Period
- 240-week, optional Open-Label Extension Period
- 30-day Follow-up Period

Per sample size calculations, a total of 90 adult subjects with classic CAH were planned to be randomized into the 76-week Treatment Period. Subjects on dexamethasone at the initial Screening Visit who agree to convert to a non-dexamethasone regimen will enter the GC Conversion Period for conversion to and stabilization on a non-dexamethasone regimen as determined by their physician. Subjects enrolled under protocol amendment \leq version 6 could also complete the GC Conversion Period to convert and stabilize to Sponsor supplied GC regimens, hydrocortisone (3 times daily) TID or prednisolone (twice daily) BID, if the subject was not on one of these regimens at screening. Subjects enrolled under and after protocol amendment 7, who are not on dexamethasone at screening, will continue on their current GC regimen at screening without the need for conversion to a standardized GC regimen prior to entering the treatment period. Permitted GC regimens include either monotherapy or combination therapy of the following GC types, hydrocortisone, hydrocortisone acetate, prednisone, prednisolone, or methylprednisolone.

Upon completion of the Screening period and GC Conversion Period, if applicable, subjects who continue to meet eligibility criteria will enter the randomized, Double-Blind, Placebo-Controlled Treatment Period. Subjects will be randomized in a 1:1 ratio to receive either tildacerfont at a dose of 200 mg QD (once a day) or matching placebo for the 24-week, double-blind part of the study. During this part of the study, a subject's daily GC regimen may be adjusted

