9 STATISTICAL AND ANALYSIS ISSUES

9.1 Adjustments for Covariates

The categorical, randomization stratification variables sex (0 = male, 1 = female) and baseline HCe group (<40 mg/day and \geq 40 mg/day) will be used in all efficacy analyses. Additional categorical covariates may include baseline daily GC type (0 = short-acting, 1 = intermediate acting or combination) and CAH Type (0 =simple virilizing, 1=salt-wasting). Baseline daily GC dose in HCe or BSA adjusted dose may also be included as a continuous covariate. The baseline value of continuous efficacy endpoints will be included as a continuous covariate in statistical models, such mixed model repeated measures (MMRM), analysis of covariance (ANCOVA), or logistic regression.

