12.3.3 Statistical Modeling and Testing

An MMRM model will be used to analyze the Primary Efficacy Endpoint. The model will comprise the change from baseline as the dependent variable; randomized treatment group (0: placebo, 1: tildacerfont), visit (Weeks 3, 6, 12, 18 and 24), randomized treatment by visit interaction as fixed effects; baseline value as a continuous covariate; within subject error will be modelled using an unstructured covariance matrix; sex (0: male, 1: female), baseline GC type (0: short-acting, 1: intermediate-acting or combination) and CAH Type (0 =simple virilizing, 1=salt-wasting) will also be included as fixed effects. The estimation method will be restricted maximum likelihood (REML). The principal treatment effect of interest is at 24 weeks for which the associated LSmeans, difference in LSmeans, CI and 2-sided p-value will be extracted from the model; in addition, the same will be extracted for each earlier visit.

In the event the MMRM model with an unstructured covariance structure does not converge, the following covariance structures will be used as substitution in the order below. Each subsequent covariance structure will be used only if each previous covariance structure was used and the model did not converge:

- a) Toeplitz covariance structure (assuming measurements from samples taken closer together in time are more highly correlated than those from samples taken farther apart)

- b) First order of auto-regressive [AR(1)] covariance structure (assuming measurements from samples taken closer together in time are more highly correlated than those from samples taken farther apart)
- c) Compound symmetry covariance structure (assuming equal correlation for measurements from a subject, regardless of how far apart in time when they were taken)

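### The cumulative GC dose model (exploratory endpoint 3.2) adjusts for baseline dose only through the <40/≥40 mg/day stratum and commits to no continuous baseline dose, which gives up precision

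*SAP*

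**What the plan says.** SAP 12.6.4 analyses total GC exposure by ANCOVA on the log scale: "The model will include log cumulative GC dose in HCe over baseline to 24 weeks as the dependent variable". Besides treatment and the type of GC at baseline, the explanatory terms are "the randomization strata: sex (0: male, 1: female) and baseline GC dose (in HCe, 0: < 40 mg/day, 1: ≥ 40 mg/day". All of them are entered as categories.

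Four other places bear on the choice of covariate:

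- SAP 9.1 has a general rule: "The baseline value of continuous efficacy endpoints will be included as a continuous covariate in statistical models". It has a separate optional one: "Baseline daily GC dose in HCe or BSA adjusted dose may also be included as a continuous covariate".
- The protocol synopsis (section 1.1) plans, for GC dose endpoints, an "analysis of covariance (ANCOVA) model with fixed covariates for baseline GC dose and treatment group". In the same paragraph it names the <40/≥40 grouping separately, as a factor for multiple imputation.
- The primary MMRM (SAP 12.3.3) includes the "baseline value as a continuous covariate".
- SAP 8.3.20.5 defines the cumulative dose. It adds stress doses, and for subjects who stop study drug before Week 24 it ends the sum at the last study-drug dose.

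**The concern.** At an unchanged dose, a subject's 24-week total is the baseline daily dose times 168 days. The entry range is "≥ 30 mg/day and ≤ 60 mg/day in hydrocortisone equivalents [HCe", a twofold spread, and the model reduces it to two groups. Variation in starting dose within each group goes into the error term.

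SAP 9.1 does not clearly repair this. A sum that starts on Day 1 has no baseline value of its own, so the mandatory rule does not plainly reach it, and the optional rule commits to nothing. Section 12.6.4 gives a complete model, so a programmer would fit it as written. The SAP governs where it differs from the protocol (SAP 3), and SAP 14 on changes from the protocol is still to be completed. The protocol's baseline-dose covariate has therefore been reduced to a stratum without explanation.

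SAP 5 names total GC exposure over 24 weeks as one of two measures of GC burden, and endpoint 3.2 is the one that tests it. A wider interval than necessary makes a real difference in exposure harder to see.

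**Working it through.** **What the plan states.** The documents give no power or precision figure for endpoint 3.2. They also give no SD or distribution for baseline dose, and no discontinuation rate. The nearest figures are the SDs for change in daily dose in SAP 6, which reproduce by normal approximation:

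- n = 40 per arm, difference 5, SD 6.9: 5 / (6.9 × √(2/40)) = 3.24, and Φ(3.24 − 1.96) = 0.90.
- n = 45 per arm, difference 7.25, SD 10.5: 7.25 / (10.5 × √(2/45)) = 3.28, and Φ(3.28 − 1.96) = 0.91.

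Both agree with the stated 90%, so 6.9 and 10.5 mg/day serve below as the spread of change.

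**What the stratum leaves out, with full follow-up, unchanged dose and no stress dosing.**

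- 40 v 60 mg/day: 40 × 168 = 6,720 mg v 60 × 168 = 10,080 mg, a 50% gap.
- 30 v 39 mg/day: 39/30 = 1.30, a 30% gap.

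These pairs are at or near the extremes of each group.

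Now suppose the A4 algorithm (Protocol 4.1.4.3) is followed with 5 mg steps at the earliest possible times:

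- 60 mg subject, reduced at every opportunity: 14×60 + 28×55 + 42×50 + 42×45 + 42×40 = 8,050 mg.
- 40 mg subject, increased at every opportunity: 42 × (40 + 45 + 50 + 55) = 7,980 mg.

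Even these opposite courses do not reverse the order of the totals, yet the model gives both subjects the same baseline term.

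**What truncation does.** A subject on an unchanged dose who stops at Week 6 has 42/168 = 25% of the full total. On the log scale that gap is ln 4 = 1.39, against ln 1.5 = 0.41 for the widest baseline contrast in the upper stratum. A few early stops can therefore dominate the residual.

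**Size of the gain.** The check simulated 200,000 subjects per scenario. It compared the residual variance of log cumulative dose under treatment plus stratum with the same model plus log baseline dose. Assumptions:

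- baseline between 30 and 60 mg/day, in four shapes;
- 5 mg steps at about Weeks 2, 8, 14 and 20, with a 15 mg floor;
- sex and GC type left out, because the documents give no effects for them.

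Cut in residual variance, with early-stop columns at SD of change about 7:

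| Baseline shape | SD of change about 7, all followed | SD about 10.5–11, all followed | 5% stop early | 10% stop early | 20% stop early |
|---|---|---|---|---|---|
| Uniform | 61% | 42% | 22% | 14% | 8% |
| 5 mg grid | 68% | 50% | 28% | 18% | 11% |
| Right-skewed | 55% | 36% | 22% | 14% | 9% |
| Heavily skewed to 30 | 42% | 25% | 16% | 10% | 6% |

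For example, in the uniform case with all followed, the residual SD on the log scale falls from 0.157 to 0.098, and 1 − (0.098/0.157)² = 0.61. With 10% stopping early it falls from 0.332 to 0.308, and 1 − (0.308/0.332)² = 0.14.

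Other settings widen the range. A normally distributed 24-week average change with SD 10.5 and the heavily skewed baseline gives 8% with full follow-up. Step-model settings with SD of change up to about 15 give 9–28%, 7–18% and 4–11% at 5%, 10% and 20% early discontinuation. A separate check also added an assumed 0.5 three-day stress events per subject, with SD of change about 11. It gave 18–48% with no discontinuation, then 8–20%, 5–13% and 3–8%.

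**The case against.** The strongest reply is that little is at stake. Endpoint 3.2 is exploratory, and SAP 9.6 controls type I error only for the primary and secondary endpoints. Randomisation is stratified at 40 mg/day, so the treatment estimate is not biased. The primary GC dose model already uses continuous baseline dose. SAP 9.1 allows the covariate, so this is an option left open. All of that stands, and it limits the point to precision. It does not justify leaving the option open: an optional covariate, in a section that otherwise lists its full model, invites either omission or a choice made after seeing data.

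A reader might infer more: that baseline dose largely determines the endpoint, so that adding it would bring a definite gain such as 40% less variance, with a matching sample-size equivalent and a known rise in power. The documents do not support this. They give the dose limits but no distribution within them. The inference also treats every sum as covering 168 days, whereas SAP 8.3.20.5 truncates it for subjects who stop early. Baseline dose is a strong predictor mainly among subjects followed to Week 24, so the larger gains belong chiefly to the completers analysis in 12.6.4.1.

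The synopsis also does not use the word continuous. It does list the dose group separately for imputation, which suggests that the dose itself was meant as the ANCOVA covariate.

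**Conclusion.** The point holds as an avoidable loss of precision in an exploratory analysis, and as a departure from the protocol synopsis and from the way the primary model treats baseline dose. Log baseline dose lowered residual variance in every scenario run.

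The size can only be given as a range. With complete follow-up it is roughly 8–68%, depending on the assumed baseline distribution and the SD of change. Under the SAP's own truncation rule it is roughly 4–28% for an assumed 5–20% early discontinuation, and slightly lower at the bottom end when stress doses are added. When subjects stop also matters, and the documents do not give that either. Neither bias nor any effect on the primary or secondary conclusions follows.

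**What to change.** Before unblinding, add log(baseline daily GC dose in HCe) to SAP 12.6.4 as a committed continuous covariate, and state that the completers analysis in 12.6.4.1 uses the same model. Keep treatment, sex, the <40/≥40 stratum and GC type.

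The cost is one phrase in the SAP and one degree of freedom. The baseline dose is already collected for the primary endpoint.
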